### ***8.7.1.3 Fat Harvest Stopping Rules***

The physician performing the fat harvest procedure should continuously monitor the patient for signs of significant bleeding from the puncture site(s) and overall hemodynamic stability. The tissue harvest procedure should be terminated if any of the following occur:

- Drop in systolic blood pressure < 90 mm/Hg requiring pressor support
- Profuse or uncontrollable bleeding from the puncture site(s)
- Rapid expansion of subcutaneous space at the fat cell tissue harvest site(s) related to bleeding into the subcutaneous space
- Hemoperitoneum or pneumoperitoneum
- Hemothorax or pneumothorax
- Evidence of perforation of a vascular structure that requires ligature or surgical control
- Evidence of perforation into abdominal cavity, peritoneum or gastrointestinal organ

Should any of the above occur, the fat harvest procedure should be terminated and the patient treated according to standard of care. DO NOT PROCEED WITH ADRCs ADMINISTRATION. Complete the study specific SAE form and notify the sponsor within 24 hours.

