## 4.3 Sample Size

Up to a total of 15 subjects will be enrolled. Each patient may contribute up to three qualified wound

areas for the analysis. If more than one wound is identified, each must be noncontiguous with the other(s). Therefore, between 15 and 45 wounds will be evaluated. Wound areas that have been treated with a biologic dressing such as Alloderm® or Integra® are not qualified for analysis. However, a wound area that receives excision and grafting as described in this protocol without the application of a biologic dressing may be qualified even if other wound areas in the subject are not qualified because they have been treated with a biologic dressing.

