## **5 ENROLLMENT**

### **5.1 Subject Enrollment**

Subjects are considered enrolled in this study when all of the following have occurred:

1. Written informed consent is obtained
2. All inclusion criteria and no exclusion criteria have been met
3. All screening evaluations are complete
4. Commencement of fat harvest (except for usual care control subjects who will not undergo a lipoaspirate procedure)

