## 5.2 Randomization and Subject Identification

Randomization to ADRC and usual care will occur within 2 hours prior to the scheduled surgery for STSG.

Randomization will be done via an interactive web response system (IWRS). Subjects will be randomized in a 2:1 ratio to receive intravenous delivery of either Celution® System processed ADRCs with usual care or to usual care alone.

A total of up to 15 subjects will be enrolled. Each patient will contribute up to three qualified wound areas for the analysis. If more than one wound is identified, each must be noncontiguous with the other(s). Therefore, between 15 and 45 wounds will be evaluated.

The 1st 5 subjects enrolled in active treatment will be observed for adverse events over a 7 day period. If no SAEs occur during that period, for that individual subject, the next subject enrolled in active treatment may be entered with the same 7 day observation period. The safety results of the first 5 subjects will be reviewed by the DMC and their evaluation will be used in conjunction with the clinical data collected to date, and if appropriate, to potentially remove the staggering approach to the study. Enrollment after the first 5 subjects enrolled in active treatment may continue only after the DMC has completed its safety review and recommends continuation.

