## 5.3 Stopping Rules

The study will be stopped and patient enrollment will be suspended if any of the following events occur:

1. Acute cardiovascular adverse event occurring within seventy-two (72) hours of the ADRC infusion.
2. Acute allergic or anaphylactic response within seventy-two (72) hours of the ADRC infusion.
3. Acute pulmonary adverse events such as acute respiratory distress syndrome (ARDS) and renal adverse events such as acute renal failure (ARF) within seventy-two (72) hours of the ADRC infusion.

The Sponsor will notify the DMC and FDA immediately for their review and recommendation on study continuation.

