## 11.2 Procedures for AE Reporting

Adverse events will be assessed according to the NIH Common Terminology Criteria for Adverse Events (CTCAE) v4.0 for scale grading adverse events.

All AEs (including SAEs and UADEs) will be recorded by the investigator or designee on the appropriate electronic case report form (eCRF). Events that occur prior to the tissue harvest, including those that are considered serious, are to be recorded in the medical history. Events, including SAEs, which occur after tissue harvest procedure day, are to be recorded on the AE eCRF. The investigator will evaluate the relationship of the adverse event to both the test material and study procedure as unrelated, unlikely, possibly, probably, or definitely related and will record the findings, including all pertinent details of the event on the eCRF.

The investigator shall submit to the sponsor and to the reviewing IRB a report of any UADE occurring during an investigation as soon as possible, but in no event later than 10 working days after the investigator first learns of the effect.

In addition, the Investigator or designee will report any serious adverse events occurring during this study to the Cytori Medical Monitor as soon as possible, but no later than 24 hours after the Investigator first identifies the adverse event.

The Investigator will take appropriate measures to ensure the subject's well-being and document these measures on the appropriate eCRF.

All serious adverse events experienced will be monitored until the event has resolved, any abnormal laboratory values have returned to baseline or stabilized at a level acceptable to the Investigator and Medical Monitor, or until there is a satisfactory explanation for the changes observed.

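### A serious fat-harvest injury cannot meet any study-level stopping trigger in Protocol 5.3, so it starts no immediate DMC/FDA notice and, if the stagger is lifted, no automatic enrolment hold

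*Protocol*

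**What the plan says.** **Study-level rule (5.3).** The study stops and enrolment is suspended on any of three kinds of event. The first reads "Acute cardiovascular adverse event occurring within seventy-two (72) hours of the ADRC infusion". The second (allergic or anaphylactic response) and the third (acute pulmonary or renal events) use the same 72-hour window after the infusion. The escalation step follows: "The Sponsor will notify the DMC and FDA immediately for their review and recommendation on study continuation".

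**Subject-level rule for the harvest (8.7.1.3).** The harvest is ended for pressor-requiring hypotension, uncontrolled or expanding bleeding, blood or air in the peritoneum or chest, vessel injury needing surgical control, or perforation into the abdomen or gut. The instruction is then: "DO NOT PROCEED WITH ADRCs ADMINISTRATION. Complete the study specific SAE form and notify the sponsor within 24 hours". The DMC and FDA are not named.

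**Other reporting routes.** Section 11.2 sends every SAE to the sponsor's medical monitor "no later than 24 hours after the Investigator first identifies the adverse event". It also has the investigator report UADEs to the sponsor and IRB within 10 working days; 11.1 limits UADEs to serious effects caused by or associated with the device. Section 10.8 schedules DMC reviews after 5, 10 and 15 subjects.

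**Stagger (5.1, 5.2, 10.8).** An ADRC subject counts as enrolled at "Commencement of fat harvest (except for usual care control subjects". Among the first 5 active subjects, each is observed for 7 days: "If no SAEs occur during that period, for that individual subject, the next subject enrolled in active treatment may be entered". Enrolment beyond those 5 needs a DMC recommendation. The DMC's review is also used "and if appropriate, to potentially remove the staggering approach to the study".

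**The concern.** The experimental strategy has two parts, harvest and infusion. Section 4.6.1 names adverse events from both as the primary safety endpoint, and section 9.10 says that the safety of liposuction in burn patients is not established. The study-level stopping rule nevertheless starts its clock only at the infusion. A subject injured badly enough at harvest to be denied the infusion falls outside that rule.

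The asymmetry is plain once the stagger has been lifted. An acute cardiovascular event in the 72 hours after infusion suspends enrolment and goes to the DMC and FDA at once. A gut or vessel perforation at harvest goes to the sponsor within 24 hours, and what follows is not fixed. Later subjects could be harvested before the DMC has looked at the injury.

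**Working it through.** The protocol gives no figure of its own on this point, so the check has two parts: which rules a harvest injury reaches, and how many subjects a missing hold could affect.

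**1. Rules reached by a listed harvest injury that bars infusion**

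| Safeguard | During the stagger | If the stagger is lifted |
|---|---|---|
| 5.3 stop with immediate DMC/FDA notice | Not met: no infusion | Not met: no infusion |
| Hold on the next active subject | Yes: the subject is enrolled (5.1) and has an SAE (5.2) | None stated |
| SAE notice to sponsor, 24 hours (8.7.1.3, 11.2) | Yes | Yes |
| UADE report to sponsor and IRB, 10 working days (11.2) | Only if device-associated | Only if device-associated |
| DMC review | Before enrolment passes 5 active subjects | At 10 and 15 subjects; no pause stated |

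The notice gap therefore exists at every stage. The hold gap exists only in the last column.

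**2. Subjects in the hold gap**

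- Maximum enrolment (4.3): "Up to a total of 15 subjects will be enrolled". Allocation is 2:1 (5.2).
- ADRC subjects at full enrolment: 15 × 2/3 = 10. After the first 5: 10 − 5 = 5. This assumes exact 2:1 allocation.
- At the 10-subject review, about 10 × 2/3 = 6.7 ADRC subjects have been enrolled. The 15-subject review follows the last harvest.

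**3. Chance that a hold would matter, given a lifted stagger**

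A hold protects only later subjects, so the event must occur in one of the first 4 of the 5. With event rate r per harvest:

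- P = 1 − (1 − r)^4
- Expected harvests after a first event, if nobody pauses: E = Σ r(1 − r)^(k−1)(5 − k), for k = 1 to 4

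Section 9.3 gives one related harvest SAE in 344 subjects: r = 1/344 = 0.29%, with an exact (Clopper–Pearson) 95% upper limit of 1.61%. No rate in burn patients is given, so 5%, 10% and 20% are assumptions.

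**4. Allowing for the chance of reaching that state**

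Assume that the DMC lifts the stagger only if the first 5 ADRC subjects have no harvest event. The joint chance is then (1 − r)^5 × P, and the joint expectation is (1 − r)^5 × E. At r = 5%: 0.774 × 0.185 = 0.14 and 0.774 × 0.476 = 0.37.

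| r | P, given lifted | E, given lifted | (1 − r)^5 | Joint chance | Joint expectation |
|---|---|---|---|---|---|
| 1/344 | 1.2% | 0.03 | 0.986 | 1.1% | 0.03 |
| 1.61% | 6.3% | 0.16 | 0.922 | 5.8% | 0.15 |
| 5% | 18.5% | 0.48 | 0.774 | 14% | 0.37 |
| 10% | 34.4% | 0.90 | 0.590 | 20% | 0.53 |
| 20% | 59.0% | 1.64 | 0.328 | 19% | 0.54 |

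**5. Time to react**

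Section 4.5 expects enrolment over 18 months, about 548 days. With 10 ADRC subjects that is 548 / 10 ≈ 55 days between harvests on average. Across up to 10 centers (4.4), harvests may cluster more closely.

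**6. How much five clean harvests show**

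Zero events in 5 leaves a one-sided 95% upper limit of 1 − 0.05^(1/5) = 45%. Passing the stagger does not by itself establish that harvest is safe in burn patients.

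**The case against.** The strongest reply is that the plan already protects subjects where least is known. During the stagger any SAE, with or without an infusion, fails the condition for entering the next active subject, which is broader than 5.3. The hold gap opens only if a DMC that has seen all safety data on five harvests chooses to remove the stagger, and it could keep the stagger or set conditions. The sponsor hears of any injury within 24 hours and, at about one ADRC subject every 55 days, would usually have weeks to act. The expected counts that assume no pause are therefore upper bounds. The one SAE in 344 is not shown to have occurred during harvest or to have prevented treatment. It followed a glycoprotein IIb/IIIa inhibitor, which is barred here, and earlier harvests generally took 150 to 450 mL against 100 to 150 mL now. Focusing 5.3 on the intravenous route, for which 9.10 reports no earlier burn trial, is a defensible choice.

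Most of this stands, and it keeps the point small. It does not close the gap. None of the stated routes brings the DMC and FDA in at once, and after the stagger none holds enrolment automatically. A DMC charter might add such a route, but none is shown, and the stopping rule itself is fixed in the protocol.

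A reader might infer more: that a harvest injury never holds enrolment, that the DMC would not learn of it, or that harvesting would simply go on. The text does not support these readings. Sections 5.1 and 5.2 supply a hold for the first 5 active subjects, 10.8 gives the DMC all safety data at its reviews, and nothing prevents the sponsor from pausing or escalating on its own initiative.

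**Conclusion.** The concern holds in limited form. A listed harvest injury that bars infusion cannot meet any 5.3 trigger. The immediate DMC/FDA notice is therefore missing for it at every stage. The automatic enrolment hold is missing only if the DMC removes the stagger, and then for up to 5 ADRC subjects at full enrolment with exact 2:1 allocation.

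The expected effect is small: 1.2% given a lifted stagger at the only documented rate, and roughly 14% to 20% jointly at assumed rates of 5% to 20%. The joint figures rest on the assumption that the stagger is lifted only after five harvests without an event. The chance that a later subject is actually harvested before a pause is lower still, because the sponsor may stop voluntarily and accrual is slow. The case for change rests less on these figures than on a stopping rule that leaves out one of the two named sources of the primary safety endpoint and can be repaired cheaply.

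**What to change.** Add a fourth item to 5.3, timed from the start of fat harvest whether or not an infusion follows. It should cover these events when related to the harvest:

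- blood or air in the peritoneum, or in the chest;
- vessel perforation that needs ligature or surgical control;
- perforation into the abdominal cavity, the peritoneum or a gastrointestinal organ;
- uncontrollable or expanding bleeding that meets the SAE definition in 11.1;
- hypotension requiring pressors, if judged related to the harvest.

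On any of these, suspend all enrolment and randomization and notify the DMC and FDA immediately, as 5.3 already does for its other triggers. A pause in the ADRC arm alone would not match 5.3 and would not be workable, because the arm is assigned only within 2 hours before surgery (5.2). Add a cross-reference in 8.7.1.3.

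The cost is one added item and one cross-reference, using an event list, an SAE definition and an escalation route that already exist. The downside is a possible extra enrolment pause. Requiring a link to the harvest for hypotension, and seriousness for bleeding, limits needless stops.

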### ***8.7.2 Digital Photography***

Digital photographs of the target wounds must be taken shortly after application of the STSG. Images of wounds will be taken by using the Silhouette Star System in accordance with the detailed work instruction provided in the Study Manual. Digital photographs will be taken at a fixed distance of approximately 30 - 50 cm from the wound. A reference image to identify the location of the target wound(s) with reference to anatomical landmarks should also be captured at the time of grafting. Prior to imaging, a label (with date, Subject number, and wound identification) and ruler (to indicate the longest length and width) will be placed near each wound site (within the camera's field of view) to track and identify each image. Images will be captured from directly above the wound (approximately perpendicular to the center of the wound surface) and at an oblique angle (approximately parallel to the center of the wound surface) to show scar height above adjacent skin. For the oblique images, a scale will be placed within the frame and immediately adjacent to the wound and perpendicular to the scar to allow assessment of scar height.

### ***8.7.3 ADRCs Delivery***

If subjects become hypotensive and require vasopressors to maintain organ perfusion between the collection of lipoaspirate and the intravenous introduction of ADRCs DO NOT PROCEED WITH ADRCs ADMINISTRATION.

Sterile technique should be maintained throughout the procedure. The intravenous ADRCs infusion will be administered by peripheral intravenous administration. An intravenous catheter (20 or 22 gauge) will be used to administer the ADRCs. The 5 mL output from the Celution System will be diluted to achieve 10 mL lactated Ringer's solution containing  $20 \times 10^6$  ADRCs in a sterile syringe. The syringe will be attached to the sterile macro (part # or designation) syringe filter and the contents of the syringe will be injected into the catheter slowly. The catheter will be flushed with 5 mL of lactated Ringer's solution from a separate sterile syringe.

## 8.8 Post-ADRC Administration time of first dressing change and Day 10 ( $\pm 2$ days)\*

The following assessments are to be conducted:

- Physical examination
- Vital signs
- Assessment for adverse events
- Concomitant medications
- Biomarkers
- Laboratory tests (time of first dressing change only):
  - CBC with Platelets
  - Electrolytes, alkaline phosphatase, AST, ALT, bilirubin, total protein, albumin, BUN, creatinine

The following assessments, tests and questionnaires should be conducted in the order listed below (as applicable to each visit) and prior to the other listed tests:

- Percent epithelialization of the graft (surgeon evaluation)
- Percent take of the graft\*\*
- Digital photographs of wound with ruler to indicate the longest length and width
- Wound pain VAS

\*Day 10 assessments performed only if wound dressing is being changed between days 8 and 12.

\*\*Graft take will be assessed as the area over which vascularization is evident and sufficient anchorage to the underlying tissue exists to support epidermal growth. Take will be expressed as a percentage of the area originally covered by the graft. Percent take is estimated separately for each of the grafted study sites.

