Exploratory Endpoints	
 
Transepithelial water loss at weeks 2, 3 and 4 to be performed at 2 different sites within the wound (central and peripheral)
 
Wound pain VAS (visual analogue scale) at time of first dressing change and day 10 and weeks 2, 3 and 4
 
Pruritis VAS at weeks 3, 4, 8, 12, 26 and 52
 
Patient and Observer Scar Assessment Scale (v2.0) at weeks 3, 4, 8, 12, 26 and 52
 
Skin elasticity measurement at weeks 12, 26 and 52
 
Vancouver Scar Scale at weeks 12, 26 and 52
 
Skin pigmentation and hardness at weeks 12, 26 and 52
 
ADRC cell population subtypes (FACS)
 
Biomarkers related to burn injury (such as C-reactive protein (CRP), IL-6, IL8, IL1<math>\beta</math>, interleukin-1 receptor antagonist (IL-1ra); neutrophil gelatinase-associated lipocalin (NGAL); Tumor Necrosis Factor-<math>\alpha</math> (TNF<math>\alpha</math>), and tumor necrosis factor receptor 1a (TNFR-1a)) and related to scarring (such as amino-terminal propeptide of type III procollagen, (PIIINP), TIMP1, MMP2, MMP9 and VEGF-A) will be collected at baseline (prior to treatment), days 6, and 10 and weeks 2, 3, 4, 8, and 12 post ADRC administration. Serum sample will be collected from 4 to 5 ml of whole blood that is centrifuged, separated into 500-<math>\mu</math>L aliquots, and stored at -80°C at the clinical site serum bank or central lab until use.
 
Serum biomarkers will be measured using commercial Enzyme-Linked ImmunoSorbent Assay (ELISA).
 

Statistics	
The intent-to-treat (ITT) population will include all randomized subjects. Randomization will occur on the STSG procedure day prior to liposuction. The per-treatment-evaluable (PTE) population will include all enrolled subjects who have day 6 follow-up information available.
 
The groups compared will be the subjects receiving ADRCs and STSG and the usual care controlled subjects (both grouped and stratified by mesh size). Analysis will be performed by a one way ANOVA.

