##### ***4.6.2 Key Secondary Endpoints***

- Percent epithelialization of the graft at time of first dressing change and day 10 (only if wound dressing change planned) and weeks 2, 3 and 4
- Percent take of the graft at time of first dressing change and day 10 (only if wound dressing change planned) and weeks 2, 3 and 4

Digital photography will be performed at surgery and at each follow-up visit for blinded independent review.

Graft take will be assessed as the area over which vascularization is evident and sufficient anchorage to the underlying tissue exists to support epidermal growth. Take will be expressed as a percentage of the area originally covered by the graft. Percent take should be estimated separately for each graft-treated site.

Both of the above endpoints will be evaluated by (a) visual inspection by the treating surgeon, and (b) standardized digital photography and scoring centrally by a blinded trained assessor.

- Percent of group with complete wound closure at each assessment through to 12 weeks

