### 8.3 Burn Evaluations

The physical characteristics of the selected burn areas and the graft (up to 3 per subject) as well as the subjective evaluation of symptoms will be evaluated using several assessment tools. The assessment tools are listed below and detailed information and instructions provided in the *Study Reference Manual*. Planned study days are listed below but an acceptable range of days (±) is in the schedule of events.

- Percent epithelialization at early dressing changes (estimated time of first dressing change and day 10 after graft application and at weeks 2, 3 and 4 (by surgeon evaluation and blinded independent review of standardized photographs)
- Percent take of the graft at early dressing changes (estimated time of first dressing change and day 10 after graft application (if wound dressing must be changed) and at weeks 2, 3 and 4
- Occurrence of complete wound healing at each assessment weeks 4 to 12
- Transepithelial water loss at weeks 2, 3 and 4
- Wound pain VAS at time of first dressing change and day 10 and weeks 2, 3 and 4
- Pruritis VAS at 3, 4, 8, 12, 26 and 52 weeks
- Patient and Observer Scar Assessment Scale (POSAS) at 3, 4, 8, 12, 26 and 52 weeks
- Vancouver Scar Scale at 12, 26, and 52 weeks
- Skin elasticity measurement at 12, 26 and 52 weeks (Delfin SkinElastimeter)
- Skin pigmentation (Delfin SkinColorCatch) measurement at weeks 12, 26, and 52
- Skin hardness (Delfin SkinFibrometer) measurement at weeks 12, 26, and 52

- Percent of wounds with complete wound closure at weeks 2, 4, 8 and 12
- Digital photography of treated wounds on day 1 and each follow up visit
- Biomarkers related to burn injury will be assessed from 4-5mL blood (serum) samples drawn at baseline (prior to treatment), time of first dressing change and day 10 and weeks 2, 3, 4, 8 and 12 post-ADRC administration.

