### 10.3 Data Analyses

Safety and efficacy endpoints will be summarized by treatment group using descriptive statistics (n, mean, SD, median, minimum and maximum), for quantitative variables and frequencies and percentages for categorical variables.

For quantitative efficacy variables, the change from baseline to each post-baseline time point will be analyzed using Student's t-test. For each endpoint, the treatment groups will be compared using two-sided tests at the alpha=0.05 level of significance.

The final dataset includes grafts with different mesh size (for example; 2:1 and 3:1). While the study is not powered for analysis of efficacy, data analysis for comparison between subjects receiving usual care and those receiving usual care plus ADRCs with respect to exploratory endpoints associated with healing (e.g.: percent epithelialization, pigmentation, hardness, Vancouver Scar Scale) will be stratified by mesh size (for example: 2:1, 3:1, 4:1, and all grouped).

Subjects randomized to the ADRC-treatment arm who undergo liposuction but who are not treated with ADRCs because the ADRCs do not meet release criteria may be followed up for the full duration of the study. Such subjects will be (a) included in the full data analysis for feasibility, (b) analyzed separately for safety, (c) analyzed in the ITT group for efficacy, and (d) excluded from the PTE group for efficacy.

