#### **10.5 Withdrawal, ITT, PTE**

Reasons for withdrawal pre- and post-randomization will be summarized. The treatment analyses will be performed on intent-to-treat basis as well as on a per-treatment-evaluable basis, as defined below:

Intent-to-Treat (ITT): All randomized subjects; randomization will occur on procedure day prior to the tissue harvest procedure. Subjects will be included in the analysis according to the treatment assigned if population is different than PTE.

Per-Treatment-Evaluable (PTE): All enrolled subjects who have day 5 follow-up information available.

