## 15 APPENDIX A: SCHEDULE OF PROCEDURES

	Day -2 to Day -1	Procedure Day 1	At First Dressing Change	Day 10 (±2d) 	Week 2 (±3d)	Week 3 (±3d)	Week 4 (±3d)	Week 8 (±7d)	Week 12 (±7d)	Week 26 (±14d)	Week 52 (±21d)
Informed consent	X										
Medical history (including demographics)	X										
Physical examination (including height and weight at screening)	X		X	X	X	X	X	X	X	X	X
Vital signs (BP, HR, Temp, RR)	X	X 	X	X	X	X	X	X	X	X	X
Concomitant medications	X		X	X	X	X	X	X	X	X	X
Laboratory Testing 	X	X	X								
Pregnancy test (urine)	X										
Inclusion and exclusion criteria	X										
Adverse events		X	X	X	X	X	X	X	X	X	X
Digital photography of wounds		X	X	X	X	X	X	X	X	X	X
Low Volume Lipoharvest		X									
Microbiology 		X									
ADRC dose prep and delivery		X									
% Epithelialization			X	X	X	X	X				
Biomarkers 	X		X	X	X	X	X	X	X		
% Graft Take			X	X	X	X	X				
Transepithelial water loss					X	X	X				
Wound Pain VAS			X	X	X	X	X				
Pruritis VAS						X	X	X	X	X	X
POSAS questionnaires						X	X	X	X	X	X
Vancouver Scar Scale									X	X	X
Skin elasticity measurement									X	X	X

	Day -2 to Day -1	Procedure Day 1	At First Dressing Change	Day 10 (±2d)	Week 2 (±3d)	Week 3 (±3d)	Week 4 (±3d)	Week 8 (±7d)	Week 12 (±7d)	Week 26 (±14d)	Week 52 (±21d)
Skin pigmentation									X	X	X
Skin hardness									X	X	X
Complete Wound Closure					X	X	X	X	X		
Randomization		X									

Day 10 assessments performed only if wound dressing is being changed between days 8 and 12. Vital signs will be monitored according to institutional procedures. Microbiological testing of dose samples (ADRCs) at baseline (prior to ADRCs administration). Biomarkers will be measured in serum from 4 to 5 ml of whole blood that is collected, centrifuged, separated into 500-µL aliquots, and stored at -80°C will be collected at baseline (prior to ADRC administration), days 5 and 10 and weeks 2, 3, 4, 8 and 12 post ADRC administration.  Laboratory testing will include CBC with Platelets, INR, PTT, Electrolytes, alkaline phosphatase, AST, ALT, bilirubin, total protein, albumin, BUN and creatinine and, for patients with diabetes only, evaluation of HbA1c levels (see Exclusion Criterion 10).

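### Percent epithelialization and graft take are to be t-tested between arms at an undated first dressing change and at a Day 10 observed only in subjects being redressed

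*Protocol*

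**What the plan says.** Protocol Section 4.6.2 makes both endpoints key secondary at first dressing change, Day 10 and Weeks 2, 3 and 4. Both carry the same condition: "Percent epithelialization of the graft at time of first dressing change and day 10 (only if wound dressing change planned") and "Percent take of the graft at time of first dressing change and day 10 (only if wound dressing change planned"). Section 8.8 and the first footnote of Appendix A tie the condition to a window: "Day 10 assessments performed only if wound dressing is being changed between days 8 and 12". The Protocol Summary lists Day 10 for these endpoints without any condition.

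The first dressing change is dated nowhere. In Appendix A its column is headed only "At First Dressing Change", and it is the only follow-up column without a plus-or-minus window. Section 8.3 speaks of the "estimated time of first dressing change and day 10 after graft application". Some other sections do use an early day, but they disagree on which. The per-treatment-evaluable population is "All enrolled subjects who have day 5 follow-up information available" in Section 10.5, while the Summary's version counts those "who have day 6 follow-up information available". Neither day is a visit in Appendix A.

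On analysis, Section 10.3 says that for quantitative efficacy variables the change to "each post-baseline time point will be analyzed using Student's t-test", with the groups compared two-sided at 0.05. Section 10.6 excludes imputation and Section 10.3.2 excludes multiplicity correction. Under Section 5.4 only the photographic assessors are blinded.

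**The concern.** A between-arm test at a visit reads as a treatment comparison only if both arms are seen at about the same time since grafting and in the groups that were randomized. Each early point can break one of these conditions.

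- **First dressing change.** Epithelialization rises with time. If dressings in one arm tend to be opened later, that arm looks better healed with no treatment effect.
- **Day 10.** The days are bounded, so the issue is who is observed. A subject not being redressed on days 8 to 12 contributes nothing, and without imputation drops out of the test. If the need for redressing follows the state of the wound, and its frequency differs by arm, the subsets are no longer comparable.

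Blinded reading of photographs does not cure either problem, because the photograph is taken at the same visit and exists only if that visit takes place. At stake is the effectiveness evidence. Section 10.3.2 says these p-values join the overall evidence on the product, and Section 10.2 says the trial is meant to inform the design of a larger one.

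**Working it through.** **Inputs from the protocol.** Up to 15 subjects at 2:1 (Sections 4.3 and 5.2) give 15 × 2/3 = 10 and 15 × 1/3 = 5. The test is two-sided at 0.05 (Section 10.3). No SD, healing rate or effect size is stated; Section 10.2 says the trial is not powered.

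**Windows.** Day 10 ± 2 gives days 8 to 12, which reproduces the range in Section 8.8, so two Day 10 assessments are at most 4 days apart. Week 2 ± 3 days gives days 11 to 17, at most 6 days apart. First dressing change has no bound.

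**First dressing change.** Assumptions: healing of 3 to 10 points per day, between-subject SD 15 to 25, and a mean gap of one day between arms.

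- Spurious difference: δ = healing rate × gap.
- Noncentrality: λ = δ / (SD × √(1/10 + 1/5)) = δ / (0.548 × SD).
- Rejection rate with no true effect: the probability that a noncentral t with 13 degrees of freedom exceeds 2.160 in absolute value.

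Example: 5 points per day, SD 20, one day. λ = 5 / (0.548 × 20) = 0.456, and the rejection rate is 7.1%.

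| δ (points) | SD 15 | SD 20 | SD 25 |
|---|---|---|---|
| 0 | 5.0% | 5.0% | 5.0% |
| 3 | 6.3% | 5.7% | 5.5% |
| 5 | 8.7% | 7.1% | 6.3% |
| 8 | 14.7% | 10.4% | 8.4% |
| 10 | 20.4% | 13.5% | 10.4% |

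A one-day gap thus gives 5.5% to 20.4%. A two-day gap at 5 points per day is the 10-point row, 13.5% at SD 20.

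**Day 10.** Simulation of 8,000 trials per row with no treatment effect, SD 20, and less-healed wounds redressed more often (correlation ρ between healing and redressing). All rates are assumptions.

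| Assessed, active / control | ρ | Mean difference, active − control | Rejection | Expected numbers |
|---|---|---|---|---|
| 80% / 80% | 0.5 | −0.22 | 4.5% | 8 vs 4 |
| 50% / 80% | 0.5 | −4.62 | 5.6% | 5 vs 4 |
| 50% / 90% | 0.5 | −6.05 | 7.3% | 5 vs 4.5 |
| 50% / 90% | 0.3 | −3.51 | 5.8% | 5 vs 4.5 |
| 50% / 90% | 0 | −0.06 | 5.0% | 5 vs 4.5 |

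There is essentially no bias when assessment rates are equal or when redressing is unrelated to healing; both conditions are needed. Even then the error rate moves little, because few subjects remain. The point estimate is affected more.

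**The case against.** **Bias is not shown.** Variable dressing days alone add noise; bias needs a systematic gap between arms, and nothing in the protocol creates one. This stands. A reader might infer that unblinded surgeons choose the timing and that the arms are therefore compared at unequal healing times. The protocol does not say who decides when a dressing is changed. That the unblinded treating team does so is a fair inference from Sections 4.6.2 and 5.4, but it is not stated. The text permits unequal timing and does not establish it.

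**Weeks 2 to 4 are not fixed days either.** Their ± 3 days is wider than the ± 2 at Day 10. This stands, and it is why the fix includes adjustment for days since grafting. Those visits do have a target day and a bound, and are not conditional on a dressing change.

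**The size is assumed, and argued for one endpoint.** This also stands. Rate, SD and gap come from outside the protocol, and the top of the range needs the steepest rate with the smallest SD. A steady daily rise is plausible for epithelialization but less clear for graft take.

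**The test is not cleanly specified.** Section 10.3 tests change from baseline, although Appendix A schedules no baseline for either endpoint, and the Summary names one-way ANOVA. With two arms, that ANOVA is equivalent to the pooled t-test, so the point is unchanged. Subjects may also contribute up to three wounds; the working treats the subject as the unit.

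**Visit assignment belongs in the SAP.** Days 11 and 12 fall in both the Day 10 and Week 2 windows. A rule for assigning such an assessment is ordinary SAP content, and its absence here is not a finding. The tests themselves and the no-imputation rule, however, are fixed in the protocol.

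**Conclusion.** The point holds, at minor severity. For two of the three key secondary endpoints, the protocol commits to unadjusted between-arm tests at one visit with no defined time and at another observed only in a subset formed after randomization. Complete wound closure is scheduled from Week 2 and is not affected.

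Under the assumptions in the working, a one-day mean gap at first dressing change raises a nominal 5% error to between 5.5% and about 20%, with 7.1% at 5 points per day and SD 20. Day 10 selection biases the comparison only if redressing depends on healing and its frequency differs by arm; the least favorable case examined gives about −6 points and 7.3%. None of these figures can be derived from the documents.

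A reader might infer that the trial's conclusion is at risk. It is not. The primary endpoint is safety and feasibility, the trial is not powered for efficacy, no decision is tied to an early p-value, and both endpoints are also assessed at Weeks 2, 3 and 4.

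**What to change.** In Section 10.3:

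- Limit between-arm tests of percent epithelialization and percent graft take to the scheduled Week 2, 3 and 4 visits (± 3 days).
- Record actual days since grafting at each assessment and use it as a covariate in a sensitivity analysis of those tests.
- Report first-dressing-change and Day 10 values descriptively by arm, with the actual day since grafting and the number assessed in each arm.

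The clinical timing of dressings does not change. The cost is protocol and SAP wording, plus the between-arm p-values at the two early time points for each endpoint. In an unpowered pilot little is lost, and the early data are still shown.
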